Mechanical circulatory support (MCS) devices improve hemodynamics in patients with AMICS and use of such devices as adjunctive therapy is supported in US guidelines (Class II a/b recommendations). It has been hypothesized that robust MCS devices such as extracorporeal membrane oxygenation (ECMO) or transvalvular pumps may improve outcomes further. Despite being available for many decades, ECMO is infrequently used because of limited availability and a high level of expertise needed for use. ECMO has historically been used by surgeons in the operating room with few cardiac catheterization laboratories having access to ECMO.

Transvalvular MCS devices however are available in over 90% of cardiac catheterization laboratories in the United States and have been approved by the FDA for use in AMICS.

Clinicians have variable experiences and expertise with MCS devices. A retrospective analysis of 15,259 patients treated with a MCS between 2009 and 2017 revealed a wide variety of outcomes associated with the use of MCS in AMICS.

Within this context the National Cardiogenic Shock Initiative (NCSI) (NCT03677180) was conceived and implemented. The aim of the study was to evaluate outcomes of patients treated with MCS using a protocolized approach emphasizing best practices. The best practices included (1) to diagnose and treat patients with AMICS as quickly as possible thereby decreasing

the duration patients remain in cardiogenic shock and attempt to decrease use and duration of vasopressors and inotropes. (2) To rapidly deliver MCS, reversing end organ hypoperfusion and preventing the neuro-hormonal cascade associated with cardiogenic shock. (3) Routine use of invasive hemodynamic monitoring with pulmonary artery catheters to guide therapy.

The final results of the NCSI study were presented at the annual SCAI scientific sessions in 2021. Between July 2016 and December 2020, a total of 406 patients were enrolled in the study across 73 sites. Patients' average age was 64±12 years, 24% were female and 67% were admitted in shock. 85% of patients were on vasopressors or inotropes, 17% had a witnessed outof-hospital cardiac arrest, 27% had in-hospital cardiac arrest, and 9% were under active cardiopulmonary resuscitation during MCS implantation. 73% of patients presented in SCAI stage C/D shock and 27% in stage E. Patients presented with an average blood pressure of 77/50, lactate of 4.8 mmol/dL and cardiac power output (CPO) of 0.67W. In accordance with the NCSI treatment algorithm, 71% of patients had MCS implanted prior to PCI. Pulmonary artery catheters were used in 93% of patients. 82% of patients presented with ST-elevation myocardial infarction with a median door to support time of 78 (IQR 54-116) mins and door to balloon time of 82 (IQR 57-114) mins. Procedural survival, survival to discharge, survival to 30-days, and survival to 1-year were 99%, 79%, 77%, 62% for patients presenting in stage C/D shock and 98%, 49%, 46%, 32% for patients in stage E shock (p<0.01). When compared to previously conducted studies in AMICS early use of MCS guided by invasive hemodynamics was associated with improved outcomes. Given the promising results, a randomized control trial is being formulated to further validate these results (RECOVIER IV).

The NCSI was an initial step in protocolizing care in AMICS. Over the past 5 years, further learnings have helped identify additional best practices that may contribute to further improving outcomes. Approximately 30-40% of patients with AMICS have concomitant right

ventricular failure (RVF), which is associated with worse morality and may therefore benefit from consideration of early right ventricular mechanical circulatory support (RV-MCS) devices. Vasopressors have been identified as being independently associated with worse outcomes and MCS escalation may lead to further improvement in outcomes. While sites participating in the NCSI were early adopters of MCS in AMICS, MCS escalation was open ended and dictated by variable local practice patterns. This contributed to the overall low rate of MCS escalation which occurred in NCSI.

In the CERAMICS study, we aim to more clearly delineate care of AMICS regarding MCS escalation and ICU management. Our goal is to enroll sites with significant experience in MCS, all of whom have the capability of MCS escalation and evaluate outcomes on ~120 patients focusing on MCS escalation decision making and ICU level management.

2. Site Selection Criteria & IRB Requirements

A total of 20 total sites will be accepted into the CERAMICS study with the goal of gathering data and outcomes of ~120 patients treated at participating centers. The study is expected to collect data for ~2 years. Prior to joining the study, each site must have broad adoption of the NCSI treatment algorithm as the standard of care for AMICS among at least 80% of the interventional cardiologists who take STEMI call, as confirmed by the site principal investigator (PI).

We are requesting a waiver of informed consent for the CERAMICS study. A Waiver of Informed consent is appropriate for the registry for multiple reasons: (1) Eligible patients are identified retrospectively after discharge from the index hospitalization, thus obtaining informed consent is not feasible. (2) Patients included in the CERAMICS registry are being treated with commercially available and FDA-approved devices, and all care is being delivered at the discretion

of their treating physicians according to standard local practice. (3) Enrolling only patients who provide informed consent would introduce substantial selection bias that reduces the validity of this research. It is critically important to track consecutive patients to assess outcomes. This is important to identify the total sample size treated and to help identify if there were particular biases on the use of MCS, escalation of MCS, etc. We will therefore also track outcomes of those not treated with MCS (i.e., exclusion form) as well as with patients treated with MCS including when care deviates from the study protocol. Clinicians will not be contacted about the care they deliver to patients at any time during the study, and the care will be delivered routinely at participating hospitals.

Patients presenting with AMICS are critically ill, with >40% of patients presenting in cardiac arrest, patients are frequently sedated, intubated and have cognitive dysfunction. Due to the critical nature and extremes of patients with AMICS, we are requesting a full waiver of informed consent and HIPAA authorization from the IRB for data collection and submission under the guidelines of 45 CFR 46.116(f) and 45 CFR 64.512(i)(2)(ii).

All study data collection is occurring retrospectively at each time-point only using EMR, and there will be no contact between study personnel and patients. Patients will be discharged or deceased at the time of study entry.

Sites seeking to join CERAMICS will need approval from their internal/local/system IRB, or the ability to either directly use WCG IRB or receive approval from their institutional/local/system IRB to defer to WCG IRB as the IRB of record and oversight for the study. For sites choosing to defer study oversight to a national IRB, the study will be reviewed by WCG IRB (formerly known as "WIRB" - Puyallup, WA), an independent IRB with AAHRPP accreditation and ISO 9001 certification for quality management.

All data is being collected via retrospective EMR review only - no patient contact will be made, including screening form, case report form (CRF), and the 30-day and 1-year follow-up forms. A limited data set of PHI will be collected (patient age, date of admission, date of MCS implant/explant, date of discharge/death) for the CRF or exclusion form, but no direct patient identifiers (i.e., name, date of birth, SSN, etc.) other than date of death will be collected. Study data forms will be submitted only after hospital discharge.

3. Research Procedures

3.1 Records Screening

This registry will be undertaken at sites only after an IRB has given full approval for the final protocol, screening and data collection forms, and the approval of the site PI. During participation in the study, study sites will regularly screen all acute MI patient records (STEMI and NSTEMI) for patients who presented with cardiogenic shock (AMICS) using the screening form.

4. Data Collection

All study data will be collected retrospectively after patient discharge or death at each study time point (post-hospital discharge, 30-days, and 1-year), via chart review only, on all patients who present with AMICS regardless of survival to hospital discharge. If a patient meets the study inclusion criteria on the screening form, then the following data will be collected (see Appendix 3):

Retrospective Data (from their medical records)

- Medical history
- Admission characteristics
- Procedure dates and times
- Procedure characteristics

- Diagnostic values
- Post-procedure information

Survival Data (collected via EMR review only) (see Appendix 4 and Appendix 5)

- Mortality at 30 days
- Mortality at 12 months

5. Population and Eligibility Criteria

Due to the heterogeneous cohort of patients who present with AMICS, we have defined a specific subset of patients from whom outcomes are to be collected (based upon our inclusion and exclusion criteria). We anticipated collecting data on approximately 120 adult AMICS patients at 20 hospital sites in the United States. Data collection and entry will occur after a patient has been discharged or deceased. The duration of hospital participation in this research study is anticipated to be approximately 2 years.

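### Do about 2 years of site participation leave too little time to follow about 120 patients for 1 year?

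*Protocol*

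**What the plan says.** Section 2 of the protocol sets the size: "A total of 20 total sites will be accepted into the CERAMICS study with the goal of gathering data and outcomes of ~120 patients". It then gives the length: "The study is expected to collect data for ~2 years". Section 5 repeats the patient and site numbers and adds: "The duration of hospital participation in this research study is anticipated to be approximately 2 years".

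Section 3.1 places screening inside that period: "During participation in the study, study sites will regularly screen all acute MI patient records". Section 4 says that the data are collected "at each study time point (post-hospital discharge, 30-days, and 1-year), via chart review only", for every patient with AMICS whether or not the patient survives to discharge. It lists "Mortality at 12 months" among the survival data. Section 5.1 wants the case report form within 45 days of discharge.

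Section 9 lists 1-year survival among the outcomes to be analysed. It names mortality as the primary outcome without a time point, allows interim analyses for presentations, and puts the final analysis of all data at the end of the study. No section gives a closing date for enrolment, a data cut-off or an expected accrual rate.

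**The concern.** The 1-year form is completed by site staff from the chart, so it seems to belong both to data collection and to hospital participation, each put at about 2 years. Screening also runs during participation. If patients were enrolled throughout the 2 years, those from the second year would reach 12 months only after their hospital's participation had ended. The statements then fit only if enrolment closes near month 12, which the protocol neither states nor excludes.

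That early close asks for 6 patients per site in one year. The only accrual record in the document is that of the National Cardiogenic Shock Initiative (NCSI), which averaged 5.6 per site in total over a much longer calendar period. If accrual were slower than hoped and chart review stopped at 2 years, the 1-year survival estimate would rest on fewer patients than the planned 120 or so.

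**Working it through.** **Inputs.** 120 patients, 20 sites and about 2 years (Sections 2 and 5); last time point 12 months (Section 4). For NCSI (background section): 406 patients, 73 sites, July 2016 to December 2020, which is 54 months or 4.5 years; 73% of patients in stage C/D and 27% in stage E; 1-year survival 62% and 32%; 30-day survival 77% and 46%. The protocol gives no derivation of the 120 or of the 2 years, so there is no planned figure to reproduce beyond 20 × 6 = 120.

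**What each reading of 2 years requires.** Rate needed = 6 / (enrolment in years). Last 1-year status = enrolment + 12 months. With even enrolment, the number admitted by month 12, and so with 12 months of potential follow-up at month 24, is 120 × 12 / (enrolment in months).

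| Enrolment | Patients per site-year | Last 1-year status | 12 months of potential follow-up at month 24 |
|---|---|---|---|
| 12 months | 6 | month 24 | 120 |
| 18 months | 4 | month 30 | 120 × 12/18 = 80 |
| 24 months | 3 | month 36 | 120 × 12/24 = 60 |

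**What NCSI says about accrual.** Per site: 406/73 = 5.56 in total. A yearly rate needs the mean time T that a site was open, which the document does not give. The rate is 5.56/T, and 20 sites would enrol 20 × 5.56/T in 12 months.

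| T assumed (years) | Per site-year | 20 sites, 12 months |
|---|---|---|
| 4.5 | 1.24 | 25 |
| 2.25 | 2.47 | 49 |
| 1 | 5.56 | 111 |

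NCSI would match 6 per site-year at T = 5.56/6 = 0.927 years, about 11 months. The range runs from far too slow to nearly enough, so the comparison does not decide the matter.

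**Precision if follow-up were cut at month 24.** Assumed 1-year mortality from the NCSI stage mix: 1 − (0.73 × 0.62 + 0.27 × 0.32) = 0.461. The 95% half-width is 1.96 × √(0.461 × 0.539 / n), which gives 8.9 points for n = 120, 10.9 for n = 80 and 12.6 for n = 60. These losses need three things together: enrolment longer than 12 months, chart review stopped at month 24, and an analysis that discards everyone admitted after month 12. The protocol states none of them. An analysis that used partial follow-up would lose less: on the same figures 30-day mortality is 1 − (0.73 × 0.77 + 0.27 × 0.46) = 0.314, so 0.314/0.461, or about 68% of 1-year deaths, fall within 30 days.

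**Earlier time points.** Even with 24 months of enrolment and a cut at month 24, 120 × 23/24 = 115 patients would have reached 30 days.

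**The case for a change.** The best case for a change is that either reading of the 2 years leaves a sentence to tidy. If the period includes follow-up, screening cannot run throughout participation and an enrolment close should be named. If it is enrolment only, data collection and participation run to about 3 years and the stated durations are a year short. Adding past patients does not help much, since a site starts only after IRB approval and the case report form is due within 45 days of discharge. Durations belong in a protocol, and the edit would cost a few sentences.

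What stands is that the split is not written down. It does not follow that the plan goes wrong. The numbers and durations are all marked as approximate, and the statements can be met together. The 1-year status comes from the electronic record without patient contact, so a later review adds little work for a site.

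The NCSI comparison carries less weight than it seems to. It sets a one-year requirement beside a total collected over an unknown open time per site. CERAMICS sites are chosen for MCS experience and broad adoption of the treatment algorithm, so faster accrual is possible. It might also be noted that NCSI enrolled to December 2020 ("Between July 2016 and December 2020, a total of 406 patients were enrolled in the study across 73 sites") and reported 1-year survival at a 2021 meeting, so some of its last patients may have lacked a full year of follow-up. That concerns another study, turns on a meeting date the document does not give, and says nothing about how CERAMICS will handle its own follow-up.

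**Conclusion.** No change is needed. The protocol leaves open whether about 2 years includes the last patient's 1-year chart review; depending on the answer, enrolment closes near month 12 at 6 patients per site-year, or the last 1-year status falls near month 36 at 3 per site-year. Neither answer alters what is measured, on whom, or how it is analysed. Followed as written, Section 4 obtains the 1-year status on all patients and Section 9 analyses all data at the end of the study, so the 1-year result is sound under both timetables. The primary outcome carries no time point, and in-hospital and 30-day mortality are almost untouched in any case.

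This rests on reading the approximate 2 years as a planning estimate that yields to the stated 12-month time point. An explicit rule ending chart review at month 24 would make the precision loss real, but the protocol contains no such rule. Handling of incomplete follow-up may also be covered in a statistical analysis plan that is not at hand.

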5.1. Inclusion Criteria

AMICS patients who meet the following inclusion criteria, and none of the exclusion criteria, will have a case report form (CRF) completed and submitted within 45 days of hospital discharge:

- Diagnosis of acute myocardial infarction (AMI) with ECG and/or biomarker evidence of S-T elevation myocardial infarction (STEMI) or non-S-T elevation myocardial infarction (NSTEMI).
- 2. Cardiogenic shock is defined as the presence of at least two of the following:
 - a. Hypotension (systolic blood pressure ≤90 mm Hg, or inotropes/vasopressors to maintain systolic blood pressure ≥90 mmHg).

- b. Evidence of end organ hypoperfusion: elevated serum lactate levels (venous or arterial), cool extremities, oliguria/anuria.
- c. Hemodynamic criteria represented by a cardiac index of $< 2.2 \text{ L/min/m}^2$ or a cardiac power output ≤ 0.6 watts.
- 3. Patient is supported with a transvalvular MCS as the initial MCS device.
- 4. Patient undergoes PCI within 12 hours of hospital presentation.

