5.2. Registry Exclusion Criteria

AMICS patients who meet any of the following study exclusion criteria will have a limited set of data collected via a single-page Patient Exclusion Form completed and submitted within 45 days of hospital discharge, which includes the reason for exclusion, date of index PCI, and assessment of patient survival to hospital discharge:

- 1. Evidence of Anoxic Brain Injury
- 2. Unwitnessed out of hospital cardiac arrest or any cardiac arrest in which return of spontaneous circulation (ROSC) is not achieved within 30 minutes
- 3. IABP placed prior to MCS
- 4. Septic, anaphylactic, hemorrhagic, and neurologic causes of shock
- Non-ischemic causes of shock/hypotension (pulmonary embolism, pneumothorax, myocarditis, tamponade, etc.)
- 6. Active bleeding for which MCS is contraindicated
- 7. Recent major surgery for which MCS is contraindicated
- 8. Mechanical complications of AMI (acute ventricular septal defect (VSD) or acute papillary muscle rupture)
- 9. Known left ventricular thrombus for which MCS is contraindicated

- 10. Mechanical aortic prosthetic valve
- 11. Contraindication to intravenous systemic anticoagulation which precludes placement of MCS.

6. Risks/Benefits of and Alternatives to Patient Participation

This is not a treatment study. This is a single-arm registry that captures data generated during procedures which are considered standard of care using FDA-approved technologies.

There are no risks other than breach of confidentiality. To mitigate this risk, only a limited set of data directly related to the research will be captured, and all data will be stored in a secure REDCap database (please see below).

7. Data Management

Data collected from the participating sites will be securely stored and managed at Henry Ford Hospital in Detroit, Michigan. Electronic data will be stored and managed in a secure REDCap study database hosted through the Henry Ford Health System Department of Public Health Sciences in Detroit, Michigan. REDCap (Research Electronic Data Capture) is a secure, web-based application designed to support data capture for research studies. A study-specific database was created solely for CERAMICS study that includes only the specific data fields that pertain to the data points collected on the case report form (CRF) or Patient Exclusion Form (PEF) (see Appendix 3).

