For patients who present to affiliated hospitals with AMICS but are excluded from a CRF (see section 5.2), a Patient Exclusion Form will be submitted to track the reasons for exclusion (see Appendix 3).

The CRFs and Patient Exclusion Forms from an individual site will be transmitted to the lead site, Henry Ford Hospital, via secure email and accessed only on hospital-approved, password-protected computers and stored on a password-protected and encrypted OneDrive system by Microsoft. Access to the OneDrive system and the REDCap database will be managed at Henry Ford Hospital by the NCSI coordinator and the investigators of the study via hospitalapproved, password-protected computers inside locked offices in Henry Ford Hospital.

8. Access to Patient Information

The following will have access to the de-identified patient medical information, and any necessary research contracts and Data Use Agreements will be completed for each participating site.

Henry Ford Hospital – Detroit, Michigan CERAMICS team:

- **Principal Investigators**
- Co-Investigators
- Study Research Coordinator(s)
- Research Nurse(s)
- Research Assistant(s)
- Data Coordinator(s)
- Statistician, based at Henry Ford Hospital

9. Analysis and Publication of Data

There will be planned interim analysis of the data for the purpose of presentations, as well as a final analysis and submission for publication of all data at the end of the study.

Demographics, admission characteristics, procedural characteristics, clinical characteristics, procedural outcomes, in-hospital outcomes, disposition, 30-day survival and 1-year survival will be analyzed. The primary outcome of the study will be to assess mortality in AMICS at study sites with the ability to implant, and if needed, escalate MCS. The CERAMICS study is an observational study and as such prone to bias, confounding and thus causality should not be inferred. However, research in AMICS is difficult to perform and there is significant heterogeneity in care. Thus, even observational data, despite its limitations, can be practice changing and valuable to the care of this high-risk cohort.¹⁰

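### Inclusion 3 enters only patients in whom transvalvular support was achieved, so failed first insertions get no CRF and no 30-day or 1-year mortality, and the exclusion form does not clearly catch them

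*Protocol*

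**What the plan says.** - **Entry.** Inclusion 3 in Protocol section 5.1 is "Patient is supported with a transvalvular MCS as the initial MCS device". Inclusion 4 separately requires PCI within 12 hours of presentation. Neither mentions an attempt, and "supported" is not defined.
- **Who gets the full data.** "AMICS patients who meet the following inclusion criteria, and none of the exclusion criteria, will have a case report form (CRF) completed". Section 4 ties the remaining data, including 30-day and 12-month mortality, to meeting the inclusion criteria.
- **Who gets the exclusion form.** Section 2 says "We will therefore also track outcomes of those not treated with MCS (i.e., exclusion form"), and in the same sentence extends tracking to "patients treated with MCS including when care deviates from the study protocol". Section 5.2 triggers the form by any of eleven listed criteria, none of which is a failed insertion. Section 7 refers back to 5.2. The form holds limited data, "which includes the reason for exclusion, date of index PCI, and assessment of patient survival to hospital discharge".
- **Purpose.** Section 2 says "It is critically important to track consecutive patients to assess outcomes", in order to establish how many were treated and whether use of MCS was biased. Section 9 states: "The primary outcome of the study will be to assess mortality in AMICS at study sites with the ability to implant, and if needed, escalate" (the object is mechanical support). It also lists procedural outcomes for analysis.
- **Timing.** Section 2 says patients are already discharged or dead when they enter the study.

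**The concern.** Whether the pump was successfully placed is known only after the decision to use it. A cohort entered on success leaves out patients who were managed the same way up to the point of failure. If they die more often than those who were supported, the reported mortality is too low and procedural survival too high.

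Retrospective entry adds to the problem. Since "supported" is undefined, about 20 sites must each decide whether a brief or partial insertion counts, and they do so when the outcome is already in the chart.

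At stake are the denominator of the primary outcome, and the protocol's own aim of tracking consecutive patients so that the number treated is known.

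**Working it through.** **Step 1: follow a failed first attempt through the protocol.**

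| Patient | CRF and 30-day/1-year mortality | Exclusion form |
|---|---|---|
| Attempt fails, no other MCS, PCI done | No (inclusion 3) | Section 2: yes, as not treated with MCS. Section 5.2: no listed reason |
| Attempt fails, another MCS device used, PCI done | No (inclusion 3) | Section 2: not covered by the not-treated clause, because MCS was given; the deviating-care clause would keep the patient in, but inclusion 3 bars the CRF. Section 5.2: no listed reason |
| Dies during insertion, before PCI | No (inclusion 4, whatever inclusion 3 says) | Section 5.2: no listed reason |

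The first two rows are lost through inclusion 3. The third is lost through inclusion 4. This route is open because support often comes first: the protocol's background reports that 71% of patients in the predecessor study (NCSI) had MCS implanted before PCI. Where an exclusion form is filed, mortality after discharge is still not collected.

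**Step 2: size for 30-day mortality.** The protocol states no mortality target, failure rate or precision, so there is no figure of its own to reproduce. The NCSI results in the background serve as a stand-in for supported patients.

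- Stage mix: 73% C/D, 27% E. 30-day survival: 77% and 46%.
- m = 1 − (0.73 × 0.77 + 0.27 × 0.46) = 1 − (0.5621 + 0.1242) = 31.4%.
- Let a share f of attempts fail, with mortality q. All-attempt mortality = (1 − f)m + fq, so the understatement is f(q − m). Both f and q are assumptions.

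| f | q | All attempts | Understatement (points) |
|---|---|---|---|
| 2% | 50% | 0.98 × 0.3137 + 0.02 × 0.50 = 31.7% | 0.02 × (0.50 − 0.3137) = 0.4 |
| 5% | 80% | 0.95 × 0.3137 + 0.05 × 0.80 = 33.8% | 0.05 × (0.80 − 0.3137) = 2.4 |

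Beside 120 supported patients, these rates mean 120f/(1 − f), or about 2 and 6 failed attempts. Over a wider range, f from 1% to 10% and q from 54% (the NCSI stage E figure) to 90%, the understatement runs from 0.2 to 5.9 points. If q = m it is zero.

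**Step 3: compare with sampling error.** The 95% half-width at n = 120 is 1.96 × √(0.3137 × 0.6863 / 120) = 8.3 points.

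**Step 4: procedural death.** Pooled NCSI procedural mortality is 1 − (0.73 × 0.99 + 0.27 × 0.98) = 1.3%, or about 120 × 0.0127 = 1.5 deaths in 120 patients. Against so small a count, one or two procedural deaths among failed attempts would be a large relative change. Whether any would occur cannot be told from the protocol.

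**The case against.** **A device-treated cohort is a legitimate registry design.** Section 5 says a specific subset was chosen, section 1 puts the focus on escalation and ICU care, section 6 says this is not a treatment study, and section 9 disclaims causal inference. A reader might infer that the primary outcome concerns an implant strategy, which would require every attempt to be counted. The text does not support that: "with the ability to implant, and if needed, escalate MCS" describes the study sites, and no such strategy is defined. This part of the objection stands. It does not dispose of the point, because a descriptive mortality figure also needs a clear denominator and section 2 asks for consecutive tracking.

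**Failed insertions need not vanish.** Section 2 promises an exclusion form for those not treated with MCS, with survival to discharge. This stands in part. The route does not cover a patient switched to another device, is not matched in 5.2, and stops at discharge. The forms in the appendix are not shown, so whether failed insertion is a coded reason there cannot be judged.

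**Some tempting statements go too far.** A reader might infer that procedural survival is near 100% by definition, or that failures fall on the sickest patients. Deaths in the laboratory after support begins still count, and the documents say nothing about who fails insertion. Implant success by site is not a stated objective either.

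**The effect is small.** It lies within sampling error at 120 patients. That is true, but it is a systematic error, and a larger sample would not remove it.

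**Conclusion.** The point holds as a defect in the cohort definition. On its plain wording, inclusion 3 drops a patient with a failed first insertion who still has PCI, and sections 2 and 5.2 do not agree on whether the exclusion form records that patient. The wording follows directly from the protocol; the direction and size of the bias do not. An understatement of 0.4–2.4 points in 30-day mortality rests on an assumed failure rate and an assumed mortality after failure, with NCSI standing in for supported patients. It is well inside the ±8.3 points of sampling error and would not by itself change how the result is read. The case for acting is that the repair is cheap and the denominator is otherwise left to site judgement after the outcome is known.

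**What to change.** 1. Reword inclusion 3 to: *insertion of a transvalvular MCS device was attempted as the first MCS device*. Add one CRF field for whether support was established, with a definition of that term.
2. Report mortality for all attempts, with successfully supported patients shown separately.
3. Rewording inclusion 3 does not recover patients who die during insertion before PCI, because inclusion 4 removes them. Add attempted insertion without PCI as a coded reason on the Patient Exclusion Form, and report those deaths beside the main estimate.
4. Reconcile section 2 with section 5.2 on who receives the exclusion form.

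Cost: a wording change, one CRF field, one exclusion code, a few extra CRFs (about 2 to 6 under the assumed failure rates), and a slightly higher reported mortality if failed attempts do worse.
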